4.5.2. Blood-based biomarkers

Blood-based biomarkers including the ones shown below are measured at baseline and weeks 4, 8, 12, 24, 36, 52, 64, and 76.

- Neurofilament Light chain (NfL)
- Phosphorylated tau (P-tau181 and P-tau217)
- Glial fibrillary acidic protein (GFAP)
- Aβ levels (Aβ 1-42 and 1-40)
- Soluble triggering receptor expressed on myeloid cells 2 (sTREM2)
- High sensitivity C-reactive protein (hsCRP)
- Other blood biomarkers when results become available.

To evaluate the change from baseline difference by treatment groups, an MMRM analysis will be used to compare change from baseline at each post-baseline timepoint for each of these blood-based biomarkers. The model will include the fixed, categorical effects of treatment, visit, and treatment-by-visit interaction, as well as baseline value, baseline value-by-visit interaction and age at baseline. Visit will be considered a categorical variable with values equal to the planned visit numbers at which the blood-based biomarker is assessed. The null hypothesis is that the difference in LS mean change between the alternative treatment regimen and the standard treatment regimen equals zero. The values for these biomarkers may be log transformed to fit the normality assumption of the model.

To assess the relationship of baseline levels of these biomarkers with ARIA-E detected by standard safety MRI, after pooling all 4 dosing regimens, logistic regression model will be used with baseline amyloid centiloid, number of microhemorrhages at baseline, presence of superficial siderosis at baseline, mean arterial pressure, anti-hypertensives being predictors of such a model other than baseline biomarker values.

A logistic regression model will be used to analyze the association between biomarker changes and ARIA-E. This model will include percent change of NfL from baseline in 24 weeks, APOE e4 genotype, number of microhemorrhages at baseline, presence of superficial siderosis at baseline, baseline amyloid centiloid, mean arterial pressure, as well as anti-hypertensives. Similar analyses will be conducted to assess the association between ARIA-E incidence at Week 52 from mean percent change of NfL from baseline in the first 24 weeks. Whether or not percent change of NfL from baseline in 52 weeks can predict incidence of ARIA-E at Week 52 will be confirmed through a logistic regression model as well.

Only participants with at least 1 occurrence of ARIA-E will be included for analyses to correlate severity of ARIA-E with change of NfL scores from baseline. For instance, to correlate severity of ARIA-E at Week 24, a proportional odds model will be used. Such a model will include treatment arm, APOE e4 genotype status, number of microhemorrhages at baseline, baseline presence of superficial siderosis, baseline amyloid centiloid, mean arterial pressure, antihypertensives, and percent change of NfL from baseline in 24 weeks.

The association between other plasma-based biomarkers, like pTau, A β levels (40 and 42), GFAP, sTREM2, or hsCRP and the frequency and severity of ARIA-E will follow the same analysis plan outlined above.

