# 2.2. Background

#### ARIA

ARIA-E and ARIA-H are considered a class effect with antibody therapies directed at amyloid, and APOE £4 carriers (heterozygotes or homozygotes) have a greater risk for ARIA-E and ARIA-H than noncarriers.

Patients with ARIA are usually asymptomatic. However, ARIA may be serious or life-threatening and could lead to permanent disability or death. When asymptomatic, ARIA may be detected by routine brain MRI. When symptoms are present in association with imaging abnormalities, symptoms include, but are not limited to

- headache
- vomiting
- dizziness
- tremor
- confusion
- visual or speech disturbances, or
- alteration of consciousness.

See the IB. Section 6.1 for more details.

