4.5. Tertiary/Exploratory Endpoints Analysis

4.5.1. Exploratory MRI sequences

The table below lists exploratory MRI sequences, and pre-specified endpoints for exploratory analyses, as well as scheduled visits for exploratory endpoints. Unscheduled MRIs will be

included for analyses of exploratory endpoints. Information about four dosing regimens will be combined before performing any analysis here.

Table 4.2. Prespecified endpoints for exploratory MRI sequences.

MRI Sequences	Scheduled Visit	Endpoints
3D FLAIR	2, 4, 8, 12, 19	 ARIA-E presence ARIA-E severity White matter disease burden
3D T2	2, 4, 8, 12, 19	PVS (perivascular spaces) score in centrum semi ovale
SWI	2, 4, 8, 12, 19	 Number of new and total ARIA-H microhemorrhages Number of total ARIA-H superficial siderosis
DTI	2, 4, 8, 12, 19	 Whole cortex MD (mean diffusivity), and FW (free water fraction) Hippocampal MD and FW Whole white matter FA (fractional anisotropy)
fMRI	2	Peak activation in occipital cortex (top 200 voxels based on z-scored activation maps)
vMRI	2, 4, 8, 12, 19	 Hippocampal volume, cortical volume, ventricle volume, whole brain volume (all normalized for intracranial volume) Cortical thickness
FLAIR 3D, 3DT2, SWI	2	Vascular risk score for CAA based on Boston 2.0 Criteria

Abbreviations: ARIA = amyloid-related imaging abnormalities; CAA = cerebral amyloid angiopathy; DTI = diffusion tensor imaging; FLAIR = fluid attenuated inversion recovery; FW = free water fraction; fMRI = functional magnet resonance imaging; MD = mean diffusivity; PVS = perivascular spaces; SWI = susceptibility weighted imaging; vMRI = volumetric magnet resonance imaging.

Prediction of ARIA

Logistic regression analyses will be used to assess four types of baseline models to predict ARIA-E incidence at Week 24:

1) The model will include baseline risk factors of ARIA-E: APOE e4 genotype, number of microhemorrhages at baseline (determined by standard safety sequences), presence of superficial siderosis at baseline (determined by standard safety sequences), amyloid centiloid at baseline, mean arterial pressure, and anti-hypertensives.

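### The SAP's model of baseline blood biomarkers against ARIA-E leaves out APOE e4 genotype, so a marker that only tracks genotype can be reported as associated with ARIA-E

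*SAP*

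**What the plan says.** SAP 4.5.2 (Blood-based biomarkers) contains three kinds of ARIA-E model.

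- **Baseline level against ARIA-E.** The SAP says that "after pooling all 4 dosing regimens, logistic regression model will be used with baseline amyloid centiloid", then microhemorrhage count, and ends the list with "presence of superficial siderosis at baseline, mean arterial pressure, anti-hypertensives being predictors of such a model other than baseline biomarker values". Genotype does not appear.
- **Biomarker change against ARIA-E.** "This model will include percent change of NfL from baseline in 24 weeks, APOE e4 genotype", followed by the same five baseline covariates.
- **ARIA-E severity, among participants with an event.** "Such a model will include treatment arm, APOE e4 genotype status, number of microhemorrhages at baseline", followed by the other four baseline covariates and the biomarker change.

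The section then extends the plan to the remaining plasma markers, so the baseline covariate list carries over to them.

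For the exploratory MRI endpoints, model 1 of SAP 4.5.1 starts: "The model will include baseline risk factors of ARIA-E: APOE e4 genotype". The rest of that model is microhemorrhage count, superficial siderosis, centiloid, mean arterial pressure and antihypertensives. The primary model in SAP 4.3.2 also includes three-level genotype. Protocol 2.2 states that APOE e4 "carriers (heterozygotes or homozygotes) have a greater risk for ARIA-E and ARIA-H than noncarriers", and Protocol 6.3 stratifies randomization by genotype.

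**The concern.** The tertiary objective is to find characteristics that predict ARIA. For a blood marker, the useful question is whether it tells the clinician something that genotype does not. If genotype is left out, the biomarker coefficient takes up whatever part of the genotype effect the marker correlates with. A significant coefficient then has two readings, a marker of ARIA-E risk in its own right or a proxy for e4 status, and this model cannot separate them.

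MRI and blood markers would also be judged against different yardsticks. Model 3 of SAP 4.5.1 adds each MRI marker to a risk model that contains genotype, while the blood markers are added to one that does not. SAP 4.5.2 names eight analytes (NfL, P-tau181, P-tau217, GFAP, Aβ 1-42, Aβ 1-40, sTREM2, hsCRP). SAP 4.1 tests at two-sided 0.05 and SAP 2.1 makes no multiplicity adjustment, so a proxy result has several chances to appear.

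**Working it through.** **1. Compare the covariate lists.**

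| ARIA-E model | APOE genotype | Treatment arm |
|---|---|---|
| Primary (SAP 4.3.2) | yes | yes |
| MRI baseline risk model 1 (4.5.1) | yes | no, arms pooled |
| Baseline biomarker (4.5.2) | **no** | no, arms pooled |
| Biomarker change (4.5.2) | yes | not listed |
| ARIA-E severity (4.5.2) | yes | yes |

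The baseline-biomarker model is the only one without genotype. Its other covariates match model 1 of SAP 4.5.1 one for one. The SAP version history for version 3.0 describes changes to antihypertensives, age and weight in the exploratory and biomarker models, and gives no reason for leaving genotype out.

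**2. Inputs from the documents.** The SAP states no power or error rate for this model, so there is no figure to reproduce. From SAP section 5: Week 24 ARIA-E is 18.5% in the standard arm and 18.5% × (1 − 0.40) = 11.1% in each alternative arm, with 720 completers. The pooled rate is (18.5 + 3 × 11.1)/4 = 12.95%, so about 720 × 0.1295 = 93 events.

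**3. Inputs assumed, because the documents give none.**

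- Noncarrier/heterozygote/homozygote mix 35/50/15%.
- ARIA-E odds ratios for heterozygotes/homozygotes of 1.5/3, 2/4 or 2/6.
- Correlation ρ between biomarker and e4 count from 0 to 0.4.
- Centiloid correlated 0.2 with e4 count, with a log-odds effect of 0.2 per SD.
- One biomarker per model, and ARIA-E by Week 24.

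The mean e4 count is 0.50 + 2 × 0.15 = 0.80. Its variance is 0.50 + 4 × 0.15 − 0.80² = 0.46, so the SD is 0.68. Hence ρ = 0.2 means a shift of 0.2/0.68 = 0.29 biomarker SD per allele, and ρ = 0.4 means 0.59.

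**4. Simulation.** Logit P(ARIA-E) = arm intercept + genotype effect + 0.2 × centiloid. Intercepts were set so that the arm rates were 18.5% and 11.1% before the small centiloid term. The biomarker is ρZ + √(1 − ρ²)ε, where Z is the standardized e4 count and ε is noise, so it has no direct effect. There were 2000 trials per setting, with a Wald test on the biomarker at two-sided 0.05. Of the SAP covariates, only centiloid was kept alongside the biomarker.

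Percentage of trials declaring the null biomarker associated, without → with genotype in the model:

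| ρ | OR 1.5/3 | OR 2/4 | OR 2/6 |
|---|---|---|---|
| 0 | 5.4 → 5.5 | 4.1 → 3.9 | 5.2 → 5.1 |
| 0.1 | 5.1 → 4.4 | 6.8 → 4.6 | 8.8 → 5.0 |
| 0.2 | 10.8 → 5.0 | 13.4 → 4.6 | 19.0 → 5.2 |
| 0.3 | 16.7 → 5.0 | 23.9 → 5.0 | 37.6 → 4.8 |
| 0.4 | 24.7 → 5.6 | 39.1 → 4.8 | 56.8 → 5.2 |

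The simulation standard error near 5% is √(0.05 × 0.95/2000) = 0.5 points, so the right-hand figures are nominal for practical purposes. At ρ = 0.4 the spurious odds ratio per SD averages 1.15, 1.21 and 1.27 across the three columns, and about 1.00 with genotype.

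**5. Treatment arm.** Adding arm without genotype leaves the ρ = 0.4 rates at 24.6%, 39.8% and 57.3%. For a marker with a true odds ratio of 1.35 per SD, ρ = 0 and genotype odds ratios 2/4, power is 75.7% without arm and 76.0% with it.

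**The case against.** The analysis is tertiary, its endpoint is framed as an association, and a proxy for genotype can still be a valid marginal predictor. That is fair, and it limits the stakes. It does not explain why this one model drops a covariate that its neighbors keep, and the section does not say that a genotype-free marginal model was intended.

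Adjustment for centiloid might absorb part of the genotype signal. It might, but the simulation kept centiloid in the model and the inflation remained. Stratifying randomization by genotype does not help either: it balances genotype across arms, not across biomarker levels.

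The size is illustrative. This stands in full. Genotype mix, odds ratios and correlations are all assumed, the documents do not say that any listed marker tracks e4 status, and at zero correlation there is no inflation.

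A reader might also infer that leaving out treatment arm is a second fault of the same kind, since the arms are pooled and the power scenario gives them different rates. The documents do not support that. Arm is randomized, so it cannot confound a baseline biomarker. Pooling is a stated choice here and in SAP 4.5.1 ("Information about four dosing regimens will be combined before performing any analysis here"), and the biomarker-change model lists no arm term either. The power cost is negligible (75.7% against 76.0%).

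**Conclusion.** The point holds for APOE genotype only. The baseline-biomarker model in SAP 4.5.2 is baseline risk model 1 of SAP 4.5.1 without genotype, and nothing else in the documents restores it. It reads as a drafting omission. Followed as written, the model can report a genotype proxy as an ARIA-E association and cannot show value beyond genotype.

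Under the assumptions above, the false-positive rate runs 4-5%, 5-9%, 11-19%, 17-38% and 25-57% at correlations of 0, 0.1, 0.2, 0.3 and 0.4, against 4-6% with genotype included. The upper figures are not forecasts: they need both a strong homozygote effect and a marker well correlated with e4 status. It would be wrong to infer that a spurious finding will occur, or that the Week 24 comparison of regimens is affected. The primary model contains genotype, and no primary or secondary result depends on this analysis. The correction is worth making because it is cheap and decides what a biomarker result would mean.

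**What to change.** In SAP 4.5.2, add APOE e4 genotype (noncarrier, heterozygous, homozygous) to the predictors of the baseline-biomarker logistic model, for NfL and every other marker, so that its covariates match risk model 1 of SAP 4.5.1. The primary model is not the right template: it uses presence rather than number of microhemorrhages, amyloid terciles rather than centiloid, and neither mean arterial pressure nor antihypertensives. An arm term is optional.

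If a genotype-free model is wanted as well, say so and report the genotype-adjusted one beside it.

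The cost is one sentence and 2 degrees of freedom. Genotype is already collected, used for stratification and included in the primary model. With one marker per model, the slopes rise from 6 to 8. On about 93 expected events that is 93/8, or between 11 and 12 events per slope.

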#### Phase 2 Study AACG ARIA events

Study AACG was a Phase 2, double-blind, placebo-controlled study in participants with early symptomatic AD with intermediate brain tau burden. In Study AACG, ARIA (-E, -H, or both) was observed in a higher percentage of participants treated with donanemab, compared to participants treated with placebo. A majority of ARIA-E and ARIA-H events were first observed within 12 weeks of treatment initiation, with most events observed by 24 weeks.

ARIA-E occurred in 26.7% of participants treated with donanemab, with 6.1% of cases being symptomatic. Symptoms associated with ARIA-E included, but were not limited to, worsening of headache, altered mental status, confusion, and difficulty expressing themselves. Serious symptomatic ARIA-E requiring hospitalization occurred in 1.5% of participants treated with donanemab.

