1.1. Objectives, Endpoints, and Estimands

Objectives	Endpoints
Primary	
To assess the effect of alternative donanemab dosing regimens versus the standard donanemab dosing regimen on ARIA-E frequency	Proportion of participants with any occurrence of ARIA-E by Week 24
Secondary	
To assess the effect of alternative donanemab dosing regimens versus the standard donanemab dosing regimen on ARIA-E frequency	Proportion of participants with any occurrence of ARIA-E by Week 52
To assess the effect of alternative donanemab dosing regimens versus standard donanemab dosing regimen on brain amyloid deposition	Change from baseline in brain amyloid plaque deposition as measured by amyloid PET scan through Week 24 Week 52 Week 76
To evaluate the effect of alternative donanemab dosing regimens on ARIA events	 Proportion of participants with any occurrence of ARIA-H by Week 24 Week 52 ARIA-E and ARIA-H by severity

To assess peripheral PK and presence of anti-donanemab antibodies	 Serum PK of donanemab ADAs against donanemab, including TE-ADAs and neutralizing antibodies
Tertiary/Exploratory	
To explore characteristics that predict risk of ARIA-E and ARIA-H	 Association between exploratory MRI imaging sequences and the occurrence and severity of ARIA events Association between blood-based biomarkers and the frequency and severity of ARIA events NfL pTau Aß levels (40 and 42) GFAP sTREM2 hsCRP
To evaluate the effect of alternative donanemab dosing regimens on IRR	IRR events frequency and severity

Abbreviations: Aß = amyloid-beta peptide; ADA = antidrug antibody; ARIA = amyloid-related imaging abnormalities; GFAP = glial fibrillary acidic protein; hsCRP = high-sensitivity C-reactive protein; IRR = infusion related reaction; NfL = neurofilament light chain; PET = positron emission tomography; PK = pharmacokinetic; pTau = phosphorylated tau; sTREM2=soluble triggering receptor expressed on myeloid cells 2; TE = treatment-emergent.

Primary estimand

The primary clinical question of interest is:

What is the frequency of ARIA-E events at Week 24 in participants with early symptomatic AD treated with an alternative donanemab dosing regimen and is there a difference compared to the standard donanemab dosing regimen, regardless of discontinuation or interruption of donanemab dosing for any reason and regardless of change in background AD medication?

The estimand is described by the following attributes:

- Population Participants with early symptomatic AD

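### The biomarker-change models in SAP 4.5.2 cannot separate predictors of ARIA-E from its consequences; a Week 4 landmark with existing samples would restore the order

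*SAP*

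**What the plan says.** The exploratory objective in SAP 1.1 is "To explore characteristics that predict risk of ARIA-E and ARIA-H". SAP 4.5.2 serves it with several blood-biomarker models:

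- **Baseline level.** ARIA-E on the baseline value of each marker, with the four regimens pooled.
- **Change over 24 weeks.** Introduced with "A logistic regression model will be used to analyze the association between biomarker changes and ARIA-E". The predictor is given as "This model will include percent change of NfL from baseline in 24 weeks, APOE e4 genotype", followed by the other baseline risk factors. Treatment arm is not listed. Week 24 is the implied outcome time, because the next sentence moves on to Week 52.
- **Week 52 outcome, 24-week change.** ARIA-E by Week 52 is assessed "from mean percent change of NfL from baseline in the first 24 weeks".
- **Week 52 outcome, 52-week change.** "Whether or not percent change of NfL from baseline in 52 weeks can predict incidence of ARIA-E at Week 52 will be confirmed" by logistic regression.
- **Severity.** A proportional odds model in ARIA-E cases only, using the 24-week change. This one does include treatment arm.

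The section then applies the same plan to pTau, amyloid-beta, GFAP, sTREM2 and hsCRP. It contains no landmark, no restriction to samples taken before the event, no exclusion of earlier events and no time-dependent covariate.

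**The concern.** A characteristic that predicts risk must be measured before the event. Here the change and the event share one window, and on the protocol's account of timing most events come early in it. For most cases the later samples then follow the event. They also follow whatever the event set off: Protocol 7.1.2 allows temporary discontinuation of dosing, 6.6 allows the dose increase to be withheld, and 8.3.3.1 mentions steroids. An association could run from marker to ARIA-E, from ARIA-E to marker, or through management, and the planned model returns one odds ratio for all three. A reader of the results, knowing that the objective is prediction and that the 52-week question is to be confirmed, could take a backward association for a usable risk marker.

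Treatment arm is a separate gap. The primary hypothesis is that arm changes ARIA-E, and the repeated-measures model in SAP 4.5.2 tests whether arm changes the markers. By the plan's own hypotheses, arm could be a common cause of both.

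**Working it through.** The plan states no figure on this point to reproduce. The check sets the timings side by side and then asks how much a backward effect could matter.

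**1. Timing**

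| Item | Source | Weeks |
|---|---|---|
| Scheduled MRIs for ARIA-E by Week 24 | SAP 4.3.1 | 4, 12, 24 |
| Scheduled MRIs for ARIA-E by Week 52 | SAP 4.4.1 | 4, 12, 24, 52 |
| Biomarker samples | SAP 4.5.2 | 0, 4, 8, 12, 24, 36, 52, 64, 76 |

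Protocol 2.2 reports of the Phase 2 study: "A majority of ARIA-E and ARIA-H events were first observed within 12 weeks of treatment initiation, with most events observed by 24 weeks". It gives no percentages.

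- A Week 24 (or Week 52) sample coincides with the last MRI that counts. Apart from small differences within the visit window, every event counted is at or before that sample.
- A mean over the first 24 weeks (samples at Weeks 4, 8, 12 and 24) mixes samples from before and after the event.
- For the 24-week change against Week 52 ARIA-E, assume that cumulative incidence at Week 52 is 1.1 to 1.5 times that at Week 24. The share of events already past by Week 24 is then 1/1.1 = 91% down to 1/1.5 = 67%.

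**2. Expected events by Week 24**

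SAP Section 5 gives 720 participants completing Visit 12 (180 per arm), with rates of 18.5% in the standard arm and 11.1% in each alternative arm:

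180 × 0.185 + 540 × 0.111 = 33.3 + 59.9 = 93.2 events (12.95%).

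**3. Size of a backward effect**

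Suppose the marker has no predictive effect, but ARIA-E or its management shifts the later sample by d standard deviations. In an unadjusted comparison of 93 cases with 627 non-cases, z = d / √(1/93 + 1/627) = d / 0.111. SAP 4.1 sets two-sided 0.05.

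| Assumed shift d | z | Probability of a significant result |
|---|---|---|
| 0 | 0 | 5% |
| 0.2 | 1.80 | 44% |
| 0.3 | 2.70 | 77% |
| 0.5 | 4.50 | over 99% |

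A simulation of unadjusted logistic models (1,000 trials of 720 per scenario) agrees. The same-window model was significant in 5% to 6% of trials at no shift, 60% to 64% at 0.25 SD (median odds ratio per SD about 1.3) and over 99% at 0.5 SD (about 1.7). The shift sizes are assumptions with no source in the documents, and the planned covariates were left out.

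**4. What a landmark does**

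The same simulation with a Week 12 landmark (free of ARIA-E to Week 12, change to Week 12, later ARIA-E as outcome) rejected in 4% to 6% of trials in every scenario, with median odds ratio about 1.0. A Week 4 landmark was not simulated; it restores the order in the same way.

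Events left after Week 12 through Week 24, if 55%, 70% or 85% occur by Week 12 (assumed; the documents say only a majority):

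- 93.2 × 0.45 = 42
- 93.2 × 0.30 = 28
- 93.2 × 0.15 = 14

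The planned model has 8 coefficients: marker, two for APOE, microhemorrhages, siderosis, centiloids, arterial pressure and antihypertensives. Three for arm make 11, so 42/11 to 14/11, or 3.8 to 1.3 events per coefficient. A Week 4 landmark keeps at least these events plus those first seen between Weeks 4 and 12. The documents do not allow that number to be computed.

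**The case against.** The strongest reply is that the plan mostly calls these analyses what they are. The 24-week model and the first Week 52 model are framed as association, as is the listed endpoint. Correctly ordered analyses already exist: the baseline-level biomarker model, and the ARIA prediction models in SAP 4.5.1, which use baseline predictors only. All of this is tertiary and feeds no success criterion. These points stand, and they limit the matter to the change models. They do not cover the 52-week sentence, which speaks of predicting and confirming, or the parent objective, which change over a shared window cannot serve.

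Three further points have weight:

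- The timing statement comes from a Phase 2 study. Protocol 2.2 says the standard regimen was the one used in studies to date, while three of the four arms here dose differently early on. The split by Week 12 may therefore differ. The coincidence of the last sample with the last MRI does not depend on it.
- Confounding by arm is possible but not sized. SAP 1.2 gives the same 3500 mg total before Week 16 in all arms. Still, the severity model adjusts for arm and the incidence model does not, with no reason given.
- A Week 12 landmark with the full covariate list could be unstable at 1.3 to 3.8 events per coefficient. That is why it should not lead.

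**Conclusion.** The point holds in this form: as written, the models of ARIA-E on 24- or 52-week biomarker change cannot distinguish predictors of ARIA-E from consequences of ARIA-E or its management. This follows from the sampling and MRI schedule and from the absence of any rule that protects the order. It applies to all the listed markers and, for the 24-week change, to the severity model.

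A reader might infer more: that the analysis will report consequences of ARIA-E as predictors. The documents do not support that. They nowhere say that ARIA-E, interrupted dosing or steroids change NfL or any other marker, and with no shift the model keeps its error near 5%. The 44% to over 99% range depends on the assumed shifts of 0.2 to 0.5 SD, on an unadjusted test, and on the SAP's assumed event rates in 720 completers.

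This is a cheap improvement to an exploratory analysis. It does not touch the primary conclusion.

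**What to change.** 1. **Predictive question: lead with a Week 4 landmark.** Use change from baseline to Week 4 in participants free of ARIA-E through the Week 4 MRI, with first ARIA-E after Week 4 through Week 24, and again through Week 52, as outcome. The Schedule of Activities already places both the Week 4 blood sample and the MRI before the Visit 4 dose. Keep a Week 12 landmark as supportive only, with few covariates.
2. **Add treatment arm** to the incidence models on biomarker change, as the severity model already does.
3. **Relabel the rest.** Report the 24- and 52-week same-window models, including severity, as descriptive associations. Remove the words on predicting and confirming from the 52-week sentence. Define the 24-week change as either the value at the visit or the mean over visits.
4. **Keep the baseline-level models** as planned.

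The cost is SAP text and programming; no new data are needed. SAP 4.1 allows a change that does not alter a principal feature of the protocol to be documented in the SAP or study report without an amendment. The downside is fewer events after each landmark, hence wider intervals. A landmark restores the time order but does not by itself remove confounding.
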